Trough PD Sampling ^c		X	х	Х	х		х		Х	Refer to Appendix 2 for additional detail.
NASH/ Fibrosis Biomarkers ^c		х			х		х		х	Includes CK-18 (M30 and M65), ELF (PIIINP, TIMP-1, HA), and PRO-C3.
Intensive PK Sampling (PK/PD sub-study only)		х					Xi			Intensive PK sampling will be performed pre-dose and 1, 2, 4, 6, and 24 hours post the first dose of study drug on Week 0/Day 1, and at pre-dose and 1, 2, 4, 6, 24, 48, and 72 hours post last dose of study drug at Week 12. Patients should be instructed to hold their dose of study drug until after pre- dose and after 24-hour PK samples are collected. Refer to Appendix 2 for additional detail.
Intensive PD Sampling (PK/PD sub-study Only)		х					Xj			7α C4 and FGF19 will be collected at matching timepoints to Intensive PK sampling (above) except at Week 12 when 7α C4 and FGF19 will not be collected at 48 and 72 hours post dose. Refer to Appendix 2 for additional detail.
Clinical Laborator	y Procedure	es/Assessn	nents							
Patient Fasting	х	х	х	х	х	х	х	х	х	Patients must be in fasted state for at least 8 hours prior to blood collection and treatment administration, where applicable.

	Screening]	Freatmen	t Period ^f			Follow -Up ^b ET ^a		Notes	
Visit	Screening	Week 0	Week 2	Week 4	Week 6	Week 8	Week 12	Week 16			
Study Day		Day 1	15	29	43	57	85	113			
Schedule Window (days)	-42 days		± 3	± 3	± 3	± 3	± 3	-7 /+2		Patients discontinuing the study at any time for any reason (Early Termination) should complete the ET visit as soon as feasible and return for a Follow-Up visit 4 weeks (-7 days /+2 days) after the last dose of study drug.	
Chemistry ^e	x	x	x	x	x	x	x	x	X	Specific analytes are listed in Appendix 1. ALT and AST stability may be evaluated prior to randomization per Section 5. Increased monitoring criteria for elevated ALT and/or AST above 2×Baseline or above 5×ULN, and elevated ALP above 3×ULN are outlined in Appendix 3. A standard lipid test will be collected as part of the clinical chemistry at Screening to confirm eligibility (Appendix 1). During study treatment, lipid parameters for PD assessments listed in Table 9 of Appendix 2 will be collected and results will be blinded. HDL will remain unblinded and will be collected as part of clinical chemistry at all visits. Refer to Appendix 5 for the eGFR formula, to be calculated by central lab.	
Hematology ^c	х	Х	х	Х	Х	Х	Х	Х	x	Specific analytes are listed in Appendix 1.	

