Note: In patients in whom there is no known history of thyroid disease and who are not on thyroid hormone replacement medication, if TSH is up to 1.5 x ULN at Screening with normal free T4, 1 repeat test is allowed to confirm the elevation in TSH. If TSH and free T4 are normal upon repeat testing and there is no clinical suspicion of thyroid disease or history of elevated TSH, the patient may be included. All thyroid axis testing should be performed in the morning, approximately at the same time.

- 8. Total bilirubin > 1.2 mg/dL
- 9. Albumin < 3.5 g/dL
- 10. INR > 1.2 in patients who are not on anticoagulant therapy
- 11. ALT or AST > $5 \times ULN$
- 12. Unstable elevated ALT or AST: Patients with ALT or AST > 60 IU/L must have evidence of a stable value over at least a 2-week time period prior to randomization as evidenced by one of the following:
 - a. Comparison to a historical value, if available, obtained within 2 to 12 weeks prior to the Screening visit: Screening value must be $\leq 30\%$ higher than a documented historical value (Note: the historical value must be $\leq 5 \times ULN$)

OR

b. Repeat value at least 2 weeks after the Screening value: Repeat value should be $\leq 30\%$ higher than the value from the Screening visit, and the repeat value must be $\leq 5 \times \text{ULN}$ (Note: repeat only the analyte(s) that is/are > 60 IU/L at Screening)

Note: If the Investigator has clinical suspicion for acute liver injury in a patient for other reasons, the patient should be excluded after discussion with the Medical Monitor.

Note: The MRI-PDFF and cT1 may proceed on the basis of the initial ALT value at Screening, given all other eligibility criteria are met, but randomization should not occur prior to confirmation of ALT and/or AST stability as specified above.

- 13. ALP > 1.5 x ULN
- 14. Platelet count < 150,000 /mm³
- 15. $eGFR < 60 \text{ mL/min}/1.73 \text{m}^2$ (Refer to Appendix 5 for the eGFR formula)
- 16. Weight loss of > 5% total body weight within 3 months prior to Screening
- 17. History of a malignancy within 2 years of screening, with the following exceptions:

CONFIDENTIAL

- a. Adequately treated carcinoma in situ of the cervix
- b. Adequately treated basal or squamous cell cancer or other localized non-melanoma skin cancer
- 18. Prior or planned (during the study period) bariatric surgery (e.g., gastroplasty, roux-en-Y gastric bypass)
- 19. Type 1 diabetes

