- Antithrombotic medications defined by WHODD SDG of "Antithrombotic drugs"
- Antidiabetic medications defined by the WHODD SDG of "Drugs used in diabetes"
- Hormonal contraceptives defined by the WHODD SDG of "Drugs used in Hormonal contraception"
- Vitamin E defined by the WHODD drug codes beginning in "001105" or if "VITAMIN E" is found in the preferred drug name
- Pioglitazone or other PPARγ agonists defined by WHODD ATC level 4 A10BD and A10BG
- o GLP-1 analogues defined by WHODD ATC level 4 code (term) A10BJ (Glucagon-like peptide-1 [GLP-1] analogues)
- DPP-4 inhibitors defined by WHODD ATC level 4 code (term) A10BH (Dipeptidyl peptidase 4 [DPP-4] inhibitors)
- SGLT2 inhibitors defined by WHODD ATC level 4 code (term) A10BK (Sodium-glucose co-transporter 2 [SGLT2] inhibitors)

The following baseline laboratory tests will be summarized as continuous variables and as frequencies for categorizations described:

- Baseline ALT level (U/L):
 - $\circ \le 60 \text{ U/L versus} > 60 \text{ U/L (overall and by sex)}$
 - < 2x ULN versus $\ge 2x$ ULN to < 5x ULN
- Baseline AST level (U/L): The same subgroups as specified for ALT above will be used
- Baseline GGT level (U/L): $\leq ULN$, > ULN
- Baseline ALP level (U/L): $\leq ULN$, > ULN
- Baseline total bilirubin level (mg/dL)
- Baseline fasting HDL cholesterol (mg/dL)
- Baseline fasting LDL cholesterol (mg/dL)

CONFIDENTIAL

- Baseline fasting total cholesterol (mg/dL)
- Baseline fasting triglycerides (mg/dL)
- Baseline fasting glucose level (mg/dL)
- HbA1c (%): $< 6.5\%, \ge 6.5\%$
- Baseline platelet count $(10^9/L)$:
- Baseline free T3 (FT3)
- Baseline total T3
- Baseline free T4
- Baseline total T4
- Baseline TBG
- Baseline rT3
- Baseline FT3/rT3

Demographics and baseline characteristics will be summarized by treatment group and overall, for the Safety, Efficacy, and Per Protocol Analysis Sets.

All demographic and baseline characteristics data will be presented in by-patient data listings.

No inferential statistical comparisons will be performed.

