8.3.1. Treatment Emergent Abnormalities

Quantitative laboratory tests will be assigned grades based on National Cancer Institute Common Terminology Criteria for Adverse Events (NCI CTCAE) Version 5. For each applicable laboratory test, a treatment emergent abnormality will be defined as a post-baseline through Week 16 CTCAE grade increase of ≥ 2 grades.

The number and percentage of patients overall and by laboratory test, with any treatment emergent laboratory abnormality, CTCAE increase of ≥ 2 grades, will be presented. Similarly, the number and percentage of patients overall and by laboratory test, with CTCAE increase of ≥ 1 grade will be presented.

CONFIDENTIAL

Estimated glomerular filtration rate (eGFR) is calculated by the central lab using the Chronic Kidney Disease Epidemiology Collaboration (CKD-EPI) equation. eGFR does not have a normal range within the central lab data. A normal range will be defined as \geq 90 mL/min/1.73m2.

LDL cannot be graded via NCI CTCAE version 5. For the purposes of treatment emergent abnormalities, LDL will be graded as follows:

• Optimal: < 100 mg/dL

• Near or Above Optimal: 100 – 129 mg/dL

• Borderline High: 130 – 159 mg/dL

• High: 160 - 189 mg/dL

• Very High: > 189 mg/dL

Listings will be presented for any patient with any treatment emergent laboratory abnormality (post-baseline through Week 16 CTCAE increase of \geq 2 grades). Normal ranges provided by the central laboratory will be presented in a listing.

The number and percentage of patients meeting each criterion detailed in Table 11 will be presented. A listing will be presented for any patient meeting any of the criteria in Table 11.

Final, Version 2.0, 26JULY2023

CONFIDENTIAL

Table 11 Liver Function Tests Potentially Reflecting Hepatoxicity Liver Function Tests

Liver Function Tests	Range of Test Values
ALT or AST	\geq 3 to \leq 5 x ULN
	\geq 5 to < 10 x ULN
	≥ 10 to < 20 x ULN
	≥ 20 x ULN
Total bilirubin	> ULN
	≥ 1.5 x ULN
	\geq 2 × ULN
(AST or ALT) plus total bilirubin	\geq 3 x ULN (ALT or AST) plus \geq 1.5 x ULN
	(total bilirubin)
	\geq 3 x ULN (ALT or AST) plus \geq 2 x ULN (total
	bilirubin)
ALP	\geq 2 x ULN
ALP and total bilirubin	\geq 2 x ULN (ALP) and \geq 2 x ULN (total
	bilirubin)
	$< 2 \times ULN (ALP)$ and $\ge 2 \times ULN (total)$
	bilirubin)
	\geq 2 x ULN (ALP) and \leq 2 x ULN (total
	bilirubin)
ALT = alanine aminotransferase; AST =	aspartate aminotransferase; ULN = upper limit of

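### SAP Table 11 counts ALT/AST of 3 to 5 times ULN without asking whether the value worsened, so elevations allowed at entry are tabulated as potential hepatotoxicity

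*SAP*

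**What the plan says.** SAP 8.3.1 (Treatment Emergent Abnormalities) contains two separate rules.

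- For CTCAE-graded tests, "a treatment emergent abnormality will be defined as a post-baseline through Week 16 CTCAE grade increase of ≥ 2 grades". Increases of at least one grade are also tabulated.
- For the liver thresholds, "The number and percentage of patients meeting each criterion detailed in Table 11 will be presented", together with a listing of every patient who meets any of them. The table is titled "Liver Function Tests Potentially Reflecting Hepatoxicity". Its ALT/AST rows start at 3 times ULN. All of its rows are multiples of ULN; none is a multiple of baseline. The sentence does not state a post-baseline period or a worsening condition.

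On entry, Protocol 5.2 excludes ALT or AST only above 5 times ULN (criterion 11). Criterion 12 adds: "Patients with ALT or AST > 60 IU/L must have evidence of a stable value". SAP 6.2 accordingly plans a baseline category running from 2 to below 5 times ULN for ALT, and the same for AST.

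During the study the protocol watches the liver partly relative to baseline. The Schedule of Activities refers to "Increased monitoring criteria for elevated ALT and/or AST above 2×Baseline or above 5×ULN", and Protocol 7.1.2 and Appendix 3 use more than 2 times baseline again, including in combination with bilirubin.

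**The concern.** The study enrols patients with presumed NASH, and the protocol accepts stable transaminase elevations as part of that disease. A table headed as potential hepatotoxicity should separate those elevations from ones that arise on treatment. As written, the ALT/AST 3 to 5 times ULN row does not.

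The reverse gap also exists. A patient who rises from 1 to 2.5 times ULN exceeds 2 times baseline, the protocol's own monitoring criterion, but meets no ALT/AST row of Table 11. No output in the SAP is specified to count patients meeting that criterion.

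This matters because Protocol 2.3 reports liver enzyme elevations with both drug classes and says that neither TERN-501 alone nor the combination has been evaluated in a NASH population. Protocol Appendix 6 also says that a laboratory abnormality without signs or symptoms should not be reported as an adverse event, so asymptomatic rises may be visible only in the laboratory outputs. With 20 patients per arm, one or two extra counts change how a row reads.

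**Working it through.** The plan gives no figure to reproduce. The check has three parts.

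**1. Which rows can an unchanged, entry-eligible value meet?** Inputs: the Table 11 thresholds (SAP 8.3.1) and the entry limits (Protocol 5.2, criteria 8, 11 and 13).

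| Table 11 rows | Entry limit | Met with no change? |
|---|---|---|
| ALT/AST 3 to 5 × ULN | 5 × ULN | Yes |
| ALT/AST 5 to 10 × ULN | 5 × ULN | Only at exactly 5.0 × ULN |
| ALT/AST 10 to 20 and ≥ 20 × ULN | 5 × ULN | No |
| Rows needing ALP ≥ 2 × ULN | 1.5 × ULN | No |
| ALT/AST ≥ 3 × ULN plus bilirubin ≥ 1.5 or ≥ 2 × ULN | as above and below | Transaminase half yes |
| Rows resting on bilirubin | 1.2 mg/dL | Depends on the laboratory ULN |

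On bilirubin, the exclusion is "Total bilirubin > 1.2 mg/dL" and the laboratory ULN is not given. An unchanged 1.2 mg/dL would reach 1.5 × ULN only if ULN were at most 1.2 / 1.5 = 0.8 mg/dL, and 2 × ULN only if ULN were at most 1.2 / 2 = 0.6 mg/dL.

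**2. How do example patients count?** Compare the rule as written (3 ≤ on-study value ≤ 5) with a worsening rule (baseline < 3 and on-study value ≥ 3), in multiples of ULN.

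| Baseline | On study | As written | Worsening rule |
|---|---|---|---|
| 4.5 | 3.2 | counted | not counted |
| 4.0 | 4.0 | counted | not counted |
| 2.5 | 3.2 | counted | counted |

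As written, an improving, a stable and a worsening patient are indistinguishable in this row.

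**3. How many patients could this be?** The share p entering at or above 3 × ULN is not in the documents, so it is assumed, from 2% to 20%. Assume further that those values do not change and that no drug affects the liver. With n = 20 per arm and 140 in total:

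- expected per arm = 20p, and in total = 140p;
- P(at least one in an arm) = 1 − (1 − p)^20;
- P(a given active arm exceeds placebo by 2 or more) = Σ_b P(B = b) · P(A ≥ b + 2), with A and B independent Binomial(20, p);
- P(at least one of the six active arms does so) = 1 − Σ_b P(B = b) · P(A ≤ b + 1)^6.

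| p (assumed) | Per arm | Of 140 | ≥ 1 in an arm | Given arm ≥ placebo + 2 | Any of six arms |
|---|---|---|---|---|---|
| 2% | 0.4 | 2.8 | 0.33 | 0.04 | 0.22 |
| 5% | 1 | 7 | 0.64 | 0.13 | 0.46 |
| 10% | 2 | 14 | 0.88 | 0.21 | 0.58 |
| 20% | 4 | 28 | 0.99 | 0.28 | 0.65 |

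The last two columns show how often baseline disease alone would produce an apparent excess in the 3 to 5 × ULN row.

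**The case against.** The strongest reply is that the gap is small and other outputs cover it. Much of this stands.

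- **Scope.** Of the 13 rows, only ALT/AST 3 to 5 times ULN is clearly filled by a stable entry value. The combined rows still need raised bilirubin.
- **Rows already present.** The 5 times ULN limb of the monitoring rule is covered by the rows from 5 times upward, and any ALP above 3 times ULN falls within ALP of at least 2 times. Only the baseline-relative limb is missing.
- **Baseline-relative outputs.** The SAP plans CTCAE grade-increase counts (8.3.1), change and percent change in chemistry (8.3), ANCOVA of ALT, AST and GGT change (7.9), baseline ALT and AST categories by arm (6.2), and listings from which a stable patient can be identified. The patient going from 1 to 2.5 times ULN contributes to the change summaries and listings and, if 1 times ULN counts as normal, to the shift tables.
- **Section title.** It suggests post-baseline values, and layout is left to table shells that are not part of these documents.

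These outputs do not fully close the gap. The shift tables in SAP 8.3.5 start from normal at baseline, so they omit patients who enter elevated. The SAP 6.2 category of 2 to below 5 times ULN does not isolate 3 times and above. No summary table pairs transaminase worsening with bilirubin. A post-baseline reading would still count an unchanged or falling elevation.

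A reader might go further and infer that Table 11 as a whole is filled by baseline disease, that it hides a real liver signal, or that patients are less well protected. The documents do not support this. Most rows need worsening or depend on bilirubin. Randomization balances pre-existing elevations in expectation, so the effect is noise and dilution, not systematic bias. Monitoring during the study follows the protocol's criteria whatever the table shows. Protocol 2.3 also says that drug-induced liver injury has not been observed with either agent.

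**Conclusion.** The point holds in a limited form. Table 11 counts on absolute multiples of ULN with no worsening condition, while entry allows ALT/AST up to 5 times ULN. Unchanged or improving elevations are therefore counted in the 3 to 5 times row and can supply the transaminase part of the combined rows.

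The size cannot be derived from the documents. The range of 0.4 to 4 patients per arm rests on an assumed 2% to 20% entering at or above 3 times ULN, and on those values staying in the row. The primary and secondary efficacy analyses are unaffected. The point is worth acting on because it changes how a reported liver safety result reads, at almost no cost. Replacing the absolute ULN counts altogether would be a matter of preference and is not needed.

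**What to change.** In SAP 8.3.1 and the matching table shell:

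1. Keep the absolute ULN counts and state that they use post-baseline values through Week 16.
2. For ALT and AST, present baseline category against worst post-baseline category. SAP 8.5 already plans baseline, worst post-baseline and change categories for QTcF.
3. Add a row for the protocol's existing criterion of ALT or AST above 2 times baseline, alone and with total bilirubin above 2 times ULN. This only tabulates a criterion that the protocol already uses. State which baseline applies, since Protocol 9.4.1 averages all pre-dose laboratory values and SAP 3.8.2 takes the last one.

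Separate rows for 5 times ULN and for ALP 3 times ULN are not needed. The cost is a shell and programming change on data already collected; no visit, sample or clinical rule changes.

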8.3.2. Thyroid Axis Testing

TSH, free T3, free T4, total T3, total T4, and TBG will be collected at Baseline and Weeks 2, 6, 12, and 16, and/or ET. Estimates of the LS mean difference for the pairwise comparisons detailed in Section 7.7 with the associated standard error of the difference, and 95% CI of the difference, the standard error of the difference, and 95% CI of the difference will be presented. Summary statistics will be provided for the levels at each visit and for change from baseline by treatment groups.

8.3.3. Sex Hormones

Free and total testosterone, estradiol, FSH, and LH will be collected at Baseline and Week 12. Estimates of the LS mean difference for the pairwise comparisons detailed in Section 7.7 with the associated standard error of the difference, and 95% CI of the difference, the standard error of the difference, and 95% CI of the difference will be presented for change from baseline by treatment group and by sex.

Final, Version 2.0, 26JULY2023

CONFIDENTIAL

8.3.4. Bone Turnover Markers

The bone turnover markers sCTX and sPINP will be collected at Baseline, Week12, and Week 16. Summary statistics will be provided for each parameter at each visit and for change from baseline at each visit.

8.3.5. Shifts in Normal Range

Shift tables for each laboratory test (hematology, chemistry, and urinalysis) showing the shift from normal at baseline to abnormal at each post-baseline visit will be presented by visit. Summaries will present the number and percentage of patients with shifts by treatment group. Denominators for percentages will be the number of patients with non-missing data at the specific assessment and baseline.

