5.1. Inclusion Criteria

Patients are eligible to be included in the study only if all of the following criteria are met:

- 1. Must be 18 to 75 years of age inclusive, at the time of signing the informed consent
- 2. Male or female, willing to follow contraception requirements defined by study protocol (Appendix 7); female patients of childbearing potential must also have negative serum pregnancy test at screening, not be breastfeeding, and not plan to become pregnant during the study or within 30 days after dosing of study drug
- 3. Overweight or obese with a body mass index (BMI) $\ge 25 \text{ kg/m}^2$
- 4. NASH diagnosed by prior biopsy and/or imaging criteria as follows:
 - a. For diagnosis based on prior biopsy:
 - Step 1: Noncirrhotic NASH with fibrosis (F1, F2, or F3 based on NASH Clinical Research Network scoring system) diagnosed by historical biopsy within 1 year prior to randomization, with no subsequent treatment for NASH and stable weight (< 5% weight loss) since the time of the biopsy. Results from a previous study biopsy are permissible if drug was deemed non-therapeutic or patient received placebo.
 - ii. Step 2: Patients meeting these and all other eligibility criteria will undergo MRI and must have liver fat content by $PDFF \ge 10\%$ and $cT1 \ge 800$ msec for randomization.
 - b. For diagnosis based on imaging:
 - Step 1: Liver stiffness measured by TE of 7.6 21 kPa and CAP > 300 dB/m by FibroScan[®] within 3 months prior to Screening. (If results are available within this timeframe, assessment does not need to be performed at Screening but will be collected on Day 1. If TE and CAP were performed at Screening, these do not need to be repeated on Day 1.)
 - ii. Step 2: Patients meeting these and all other eligibility criteria will undergo MRI and must have liver fat content by $PDFF \ge 10\%$ and $cT1 \ge 800$ msec for randomization.

- 5. All patients must have MRI-PDFF $\ge 10\%$ and cT1 ≥ 800 msec
- Capable of giving signed informed consent as described in Section 10.1.2, which includes compliance with the requirements and restrictions listed in the informed consent form (ICF) and in this protocol, including ability to consistently take study drug once daily on an empty stomach

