8.1.8. Thyroid Axis Safety Monitoring

Clinical signs and symptoms of hyper/hypothyroidism are variable and should be considered when assessing participants for AEs throughout the course of the study.

Major signs and symptoms of hyperthyroidism are:

- Overt hyperthyroidism is characterized by a constellation of symptoms including anxiety, emotional lability, restlessness, irritability, psychosis, agitation, depression, insomnia, weakness, tremor, palpitations, heat intolerance, increased perspiration, or weight loss (although weight gain may also be seen due to appetite stimulation). Signs may include hyperactivity, rapid speech, eye lid lag, warm and moist skin, tachycardia, systolic hypertension, proximal muscle weakness, or hyperreflexia
- Other symptoms may include hyperdefecation, urinary frequency, atrial fibrillation, heart failure, premature atrial contractions, shortness of breath, myopathy, hypercalcemia, or osteoporosis (with prolonged thyroid hormone excess)

Major signs and symptoms of hypothyroidism are:

- Effects of slowing of metabolic processes such as slow movement and speech, delayed relaxation of tendon reflexes, bradycardia, fatigue and weakness, cold intolerance, dyspnea on exertion, weight gain, cognitive dysfunction, or constipation
- Effects of accumulation of matrix substances such as coarse skin, puffy facies and loss of eyebrows, periorbital edema, tongue enlargement, dry skin, hoarseness, or edema
- Others such as diastolic hypertension, decreased hearing, myalgia and paresthesia, depression, or arthralgia

Liver function test monitoring criteria include guidance on increased monitoring in the event of alkaline phosphatase elevation (Appendix 3), as hyperthyroidism-associated liver injury may be cholestatic in nature and present with high alkaline phosphatase levels. Study drug discontinuation guidelines for ALP elevations are included in Section 7.1.2.

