Appendix 4: Fridericia's Formula

A single 12-lead ECG will be obtained as outlined in the Schedule of Activities (see Section 1.1) using an ECG machine that automatically calculates the heart rate and measures PR, QRS, and QT intervals. QTc will be calculated using Fridericia's Formula as outlined below.

The Investigator will review the ECGs for any clinically significant abnormalities.

Fridericia's Formula:

QTc = QT/(RR^0.33) http://www.thecalculator.co/health/QTc-Calculator-385.html

Appendix 5: Chronic Kidney Disease Epidemiology Collaboration (CKD-EPI) Formula to Estimate Glomerular Filtration Rate

 $GFR = 141 \times \min(S_{cr}/\kappa, 1)^{\alpha} \times \max(S_{cr}/\kappa, 1)^{-1.209} \times 0.993^{Age} \times 1.018 \text{ [if female]} \times 1.159 \text{ [if black]}$

Abbreviations / Units:

SCr (standardized serum creatinine) = mg/dL $\kappa = 0.7$ (females) or 0.9 (males) $\alpha = -0.329$ (females) or -0.411 (males) min = indicates the minimum of SCr/ κ or 1 max = indicates the maximum of SCr/ κ or 1 age = years

Appendix 6: Adverse Events: Definitions and Procedures for Recording, Evaluating, Follow-up, and Reporting

AE Definition

- An AE is any untoward medical occurrence in a patient or clinical study patient, temporally associated with the use of study drug, whether or not considered related to the study drug.
- NOTE: An AE can therefore be any unfavorable and unintended sign (including an abnormal laboratory finding), symptom, or disease (new or exacerbated) temporally associated with the use of study drug.

Events Meeting the AE Definition

- Any safety assessment (eg, ECG, radiological scans, vital signs measurements), including those that worsen from baseline, considered clinically significant in the medical and scientific judgment of the Investigator (ie, not related to progression of underlying disease).
- A clinical condition or symptom associated with an abnormal laboratory test result (e.g. hematology, clinical chemistry, or urinalysis). An abnormal laboratory test that is not accompanied with other signs or symptoms should not be reported as an AE.
- Exacerbation of a chronic or intermittent pre-existing condition including either an increase in frequency and/or intensity of the condition.
- New conditions detected or diagnosed after study drug administration even though it may have been
 present before the start of the study.
- Signs, symptoms, or the clinical sequelae of a suspected drug-drug interaction.

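### The laboratory shift table in SAP 8.3.5 merges low and high shifts, and its eGFR row cannot register decline in patients who enter at 60-89

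*SAP*

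**What the plan says.** SAP 8.3.5 covers hematology, chemistry and urinalysis, with tables "showing the shift from normal at baseline to abnormal at each post-baseline visit will be presented by visit". It adds: "Denominators for percentages will be the number of patients with non-missing data at the specific assessment and baseline". It gives no direction and no row for patients who start outside range.

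eGFR is a chemistry test (Protocol Appendix 1, Table 7). On its range, SAP 8.3.1 states: "eGFR does not have a normal range within the central lab data". It then defines normal as 90 mL/min/1.73m² or more. Section 8.3.5 does not repeat that limit, but neither document gives another, so its use in the eGFR row is an inference, and a safe one.

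Protocol 5.2, exclusion criterion 15, excludes patients only below 60 ("Refer to Appendix 5 for the eGFR formula"). Patients at 60-89 are therefore eligible and count as abnormal at baseline. The age criterion in Protocol 5.1 reads: "Must be 18 to 75 years of age inclusive".

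**The concern.** A shift table is where a reader looks for individual patients leaving the normal range. Two features weaken it here.

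**Direction.** Protocol 8.1.8 lists, among findings that may accompany hyperthyroidism, "hypercalcemia, or osteoporosis (with prolonged thyroid hormone excess"). A calcium above range and one below range would be the same entry in 8.3.5. HDL reduction is a named TERN-101 risk (Protocol 2.3). If the laboratory's HDL range has both limits, low and high HDL also share one count. A patient who moves from low to high is not counted, because only patients normal at baseline can shift.

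**eGFR.** The range is one-sided, so direction is not the problem. The problem is where the limit sits. A stable patient measured at 92 and then 88 is a shift; a patient who falls from 85 to 61 is not. The row is noisy where function is normal and silent in patients who start with less reserve, and those patients still enlarge the denominator.

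**Working it through.** The SAP gives no expected shift rates, so there is no stated figure to reproduce. Three checks follow. The distributional inputs in checks 2 and 3 are assumptions, not taken from the documents.

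**1. How close 90 lies to ordinary values (Protocol Appendix 5 formula)**

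For a non-black man with creatinine at or above 0.9 mg/dL, eGFR = 141 × (SCr/0.9)^−1.209 × 0.993^age.

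- Age 55, SCr 0.906: eGFR 95.0. Age 55, SCr 0.948: eGFR 90.0. A rise of about 0.04 mg/dL takes him from 95 to the limit.
- Age 65, SCr 0.90: 141 × 0.993^65 = 89.3, already abnormal.
- Age 75 (below 0.9 the exponent on SCr/0.9 is −0.411): he needs SCr of about 0.745 or less to be normal.

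**2. eGFR shifts with no true change**

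Assumptions: mean 88 to 98, between-patient SD 15, within-patient SD 4 to 7, baseline at least 60. The SAP's rate per visit is

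P(baseline ≥ 90 and visit < 90) = P(baseline ≥ 90) × P(visit < 90 given baseline ≥ 90).

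| Mean | Within-patient SD | Baseline < 90 | Shift, given baseline ≥ 90 | Shift, SAP denominator |
|---|---|---|---|---|
| 98 | 4 | 29.8-29.9% | 7.3% | 0.70 × 7.3% = 5.1-5.2% |
| 88 | 7 | 52.7% | 21.3% | 0.473 × 21.3% = 10.1% |

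If SD 15 is read as the SD of observed rather than true values, the second row becomes 11.0%. A closed form supports this. With the mean at 90 and no truncation, the rate is arccos(ρ)/(2π), where ρ = (225 − 49)/225 = 0.782, which gives 10.7%. The range is thus about 5-11% per visit, or 20 × 0.05 = 1.0 to 20 × 0.11 = 2.2 patients per arm. A second set of assumptions (mean 85 to 100, within-patient CV 3-8%) gives 3-10%.

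Over the first set, 30-54% of patients enter below 90. They have zero probability of a shift in this table, whatever happens to their renal function.

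**3. Direction, for a test with a two-sided 95% range**

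Let baseline and visit values be bivariate normal with unit SD, correlation 0.5 to 0.7, limits ±1.96 and visit mean moved by d. Among patients normal at baseline:

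| d | High | Low | Undirected |
|---|---|---|---|
| 0 | 1.8-2.1% | 1.8-2.1% | 3.5-4.3% |
| +0.5 SD | 6.0-6.6% | 0.4-0.5% | 6.4-7.2% |
| −0.5 SD | 0.4-0.5% | 6.0-6.6% | 6.4-7.2% |

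On the SAP's denominator each entry is multiplied by 0.95. Opposite effects of equal size give the same undirected entry.

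**The case against.** The strongest reply is that this is one display among several, and most of the others keep direction.

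- SAP 8.3 summarizes change and percent change from baseline by arm and visit for quantitative chemistry and hematology. That covers calcium, HDL and eGFR. A fall from 85 to 61 enters that summary.
- SAP 8.3 also gives one-sided counts for CK, hemoglobin, hematocrit, platelets and WBC, and lists all safety laboratory data by patient.
- ALT has an ANCOVA of change (7.9) and upper-side criteria (8.3.1, Table 11). LDL, the protocol's own example of opposing effects, has ordered categories (8.3.1) and an ANCOVA (7.18).
- Table layouts are held in the TFL shells (SAP 3.1), which are not available here and may already separate low from high.
- eGFR noise falls on all randomized arms alike, placebo included. Protocol 2.3 names no renal risk, and Protocol 2.2.1.2 reports under 3% of a TERN-501 dose excreted unchanged in urine.

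All of this stands, and it sets the size of the point. It does not remove it. A mean change can hide a few outlying patients, and the one-sided counts do not include calcium, HDL or eGFR. The rule should also be in the SAP text, not left to the shells.

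**Conclusion.** The point holds for this table and no further. As written, 8.3.5 merges low and high shifts for tests with two-sided ranges and keeps in the denominator patients who cannot shift. Combined with the limit of 90 and entry from 60, it leaves the eGFR row unable to show decline in patients entering at 60-89, and it counts ordinary variation near 90 in about 5-11% of patients per visit. That range rests on the assumed means and SDs above. The structural part, that patients at 60-89 cannot shift, needs no assumption beyond applying the 8.3.1 limit.

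A reader might infer more, and the documents do not support it:

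- *That opposite drug effects become indistinguishable in the safety report.* The signed summaries and listings show otherwise.
- *That eGFR noise biases the arm comparison.* It affects all arms alike. With about 20 per arm it dilutes a signal and allows chance imbalance.
- *That the noise rate is 7-21% per visit, or 18-48% over six visits.* The first figure conditions on a normal baseline, which is not the SAP's denominator. The second matches no planned output, because 8.3.5 reports by visit.
- *That the grade-increase counts in 8.3.1 also lose direction.* This cannot be shown, because the documents do not reproduce the CTCAE grading.

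No efficacy conclusion is affected.

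**What to change.** In SAP 8.3.5, present low/normal/high at baseline by low/normal/high at each visit, by arm, with percentages based on the number in each baseline category. For eGFR, use ordered categories (at least 90, 60-89, below 60) at baseline by visit, and place the table next to the planned change from baseline. The change summary is still needed: a fall from 85 to 61 stays within the 60-89 category, and values near either boundary will still cross by chance.

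Replacing 90 with a single boundary at 60 would be no better. It moves the boundary noise and, under the same kind of assumptions, leaves a nearly empty row (about 0.3-1.8% of patients per visit, under half a patient per arm). A count of patients with a set percentage fall would need a threshold that the documents do not supply.

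The cost is SAP wording and table shells. The drawback is wider tables with small cells at about 20 patients per arm.
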